### 7.6.2 Sensitivity analyses on the secondary endpoints

Sensitivity analyses on the secondary endpoints will also be performed using different methods of data imputation for missing values at a particular visit if applicable, namely 1) the "shift imputation" approach; and 2) the "pattern-mixture-model imputation" approach.

The latter approach can be applied to data with monotone missing data patterns. Hence, if necessary to apply the approach, the data will be transformed into the monotone patterns by considering the

longest uninterrupted sequences of the measurements for the subjects and/or excluding a few measurement visits from modelling, to increase the number of monotone patterns in the data. In case data are re-shaped, the primary analysis MRM model will be applied to the re-shaped data as well.

### 7.7 SUBSET ANALYSES

The trial is not sized to test for the presence of treatment by subset interactions. Thus, true treatment by subset interactions will likely be missed, unless they are quite substantial. Conversely, should any particular subset of subjects seem to benefit more or less from therapy than the total population, this will not be taken as evidence of a true treatment by subset interaction, given the likelihood that such an observation could be due to chance alone. With these caveats in mind, exploratory subset analyses will be performed to identify any major effect that might be worth testing in future trials. Clinically meaningful subsets will be looked at, including stratification factors: Baseline visual acuity (< 50 vs.  $\geq$  50 ETDRS letters), Baseline geographic atrophy (<4 vs.  $\geq$  4 disc area), Pattern of Fundus Auto Fluorescence at the junctional zone of geographic atrophy (none/focal vs. banded/diffuse).

These analyses will be considered as supportive efficacy analyses and conducted without any alphalevel adjustment.

### 8 SAFETY EVALUATION

All safety analyses will be performed on the safety population. The analyses will be conducted according to the treatment that they actually received. However, subjects who have ever received an injection of Zimura will be analyzed in the Zimura group. Missing values of safety data will not be imputed and safety summaries will be based on the observed cases.

### 8.1 EXTENT OF EXPOSURE

Exposure to study medication will be evaluated for each treatment group (Zimura 4 mg, 2 mg, and 1 mg) with respect to treatment duration (= Last injection date - First injection date + 30, in days), number of subjects treated at each planned visit, total injections received, using descriptive statistics (N, mean, standard deviation, median, minimum, Q1, Q3, maximum).

### 8.2 ADVERSE EVENTS

Adverse events (AEs) will be recorded starting after the first dose of study drug and continuing until 30 days after the last dose or until the last follow-up visit required by the protocol, whichever comes later. AE data will be evaluated for each treatment group (Zimura 4 mg, 2 mg, and 1 mg).

Only first year AE data will be included in the following analyses. First year will be defined as starting after the first dose of study drug until prior to the first injection at Month 12. If a Month 12 injection does not exist, the end of first year is defined as the Month 12 visit (or target of 365.25 days after the date of first dose if no Month 12 visit) or 30 days after the last injection, whichever

is later. AEs from the first year will be defined as AEs from the start of the first dose until prior to the first injection at Month 12 or 30 days after the last dose, within the first year as defined above.

The safety analyses on AEs will be primarily based on the Treatment-Emergent Adverse Events (TEAEs), which is defined as an AE occurring after the first injection on Day 1 (day of the first planned dose of study drug) and up to and including 30 days after the last dose of study drug, within the first year as defined above.

All AEs will be coded using MedDRA (the most recent Version 18.1) terms.

- An overview of TEAEs will be provided. A second overview of TEAEs will be provided which displays the overall summary of TEAEs by the categories 'Study Eye', 'Non-Study Eye', and 'Non-Ocular'. In addition, the number and percentage of patients with TEAEs will be tabulated for each treatment group and in total by system organ class (SOC) and preferred term (PT). The number and percentage of the subjects who experienced at least one TEAE will be included. Subjects will only be counted once for each preferred term. In case that a subject experienced the same event more than once, the worst severity will be presented.
- Tabular summaries of the following AEs will be provided by SOC and PT:
  - Summary of TEAEs
  - All TEAEs regardless of the relationship to study treatment
  - All TEAEs regardless of the relationship to study treatment with frequency of  $\geq$  5% in any treatment arm.
  - TEAEs related to study treatment
  - TEAEs related to injection procedure
  - TEAEs by the maximum severity grade
  - TEAEs related to study treatment by the maximum severity grade
  - TEAEs related to injection procedure by the maximum severity grade
  - All Ocular TEAEs by study eye and fellow eye
  - Treatment related Ocular TEAEs by study eye and fellow eye
  - Injection procedure related Ocular TEAEs by study eye and fellow eye
  - Ocular TEAEs (study eye) by the maximum severity grade
  - Treatment related Ocular TEAEs (study eye) by the maximum severity grade
  - Injection procedure related Ocular TEAEs (study eye) by the maximum severity grade
  - TEAEs with high level term of cataract conditions by study eye and fellow eye
  - TEAEs leading to discontinuation of study drug

- Treatment related TEAEs leading to discontinuation of study drug
- Injection procedure related TEAEs leading to discontinuation of study drug
- Ocular TEAEs (study eye) leading to discontinuation of study drug
- TEAEs leading to death
- Treatment related TEAEs leading to death
- Injection procedure related TEAEs leading to death
- Ocular TEAEs have been defined as TEAEs linked to the "Eye Disorders" system organ class and the 'Intraocular pressure increased' preferred term.
- All AEs, including non-TEAEs, will be included in individual subject listings.
- The listings will include the subject identifier, age, sex, verbatim term, preferred term, eye (N/A/OD/OS/OU), serious (yes/no), date of onset, relative study day of onset, onset before injection, after first injection or after second injection, duration of the event (or continuing), severity (mild/moderate/severe), causality (relationship to study medication/injection procedure), action taken (study drug permanently discontinued: yes/no), treatment (yes/no), and outcome (resolved / fatal).
- The same listings will be provided separately for severe AEs, AEs leading to permanent discontinuation of the study treatment, and for AEs leading to death.

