	
(ETDRS letters) from Baseline to Month 12
 
Safety Endpoints:
 
 
• Adverse events (AEs)
 
• Vital signs (pulse, systolic and diastolic blood pressure)
 
• Ophthalmic findings (intraocular pressure [IOP], ophthalmic examination, fluorescein angiogram, FAF, and Optical Coherence Tomography [OCT])
 
• Electrocardiogram (ECG) (12-lead)
 
• Laboratory variables (blood: hematology, renal function, hepatic function, and electrolytes; urinalysis)
 

PLANNED SAMPLE SIZE:	Approximately 277 subjects will be enrolled.
SUBJECT SELECTION:	Subjects of either gender aged 50 years or greater diagnosed with geographic atrophy secondary to dry AMD.
FORMULATION:	
[REDACTED]
 
[REDACTED]
 
[REDACTED]
 
[REDACTED]
 
[REDACTED]
 
[REDACTED]
 
[REDACTED]
 
[REDACTED]
 
[REDACTED]

INVESTIGATIONAL DRUG DOSAGE:	Subjects randomized to active drug will receive 18 doses of Zimura™ at a dose of 1 mg/eye, 2 mg/eye or 4 mg/eye. Commencing with Amendment C, no new subjects will be enrolled in Part 1 of this trial.

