### 9.1.2 Treatment Regimen and Duration

Subjects randomized to active drug or Sham will receive monthly injections of Zimura™ or Sham for 18 months. Monthly doses should be administered at least 21 days apart.

- Part 1 Subjects:
  - Subjects randomized to the Zimura™ 1 mg/eye treatment arm will receive Zimura™ 1 mg/eye (50 µL) intravitreal injection.
  - Subjects randomized to the Zimura 2 mg/eye treatment arm will receive Zimura™ 2 mg/eye (100 µL) intravitreal injection.

- Subjects randomized to the Sham treatment arm will receive Sham injections.
- Commencing with Amendment C, no new subjects will be enrolled in Part 1 of this trial. Subjects in Part 1 who have received greater than or equal to 18 months of Study Drug treatment will be discontinued from the study after Amendment C.
- Part 2 Subjects:
  - Subjects randomized to the Zimura™ 2 mg/eye treatment arm will receive a Zimura™ 2mg/eye injection (100 µL) and a Sham injection
  - Subjects randomized to the Zimura™ 4 mg/eye treatment arm will receive two injections of Zimura™ 2 mg/eye. The injection volume for subjects randomized to this arm will be of (100 µL) per injection.
  - Subject's randomized to the Sham treatment arm will receive 2 Sham injections.

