### 11.3 Determination of Sample Size and Statistical Rationale

The sample size determination for this study is based on [REDACTED] screening methodology presented in Fleming and Richardson (2004). The power calculations are based on the recently released results from a clinical trial of a complement inhibitor, including the estimated precision of the estimated effects on rate of GA growth over 12 months, and including the plausible effect size for Zimura™.

A total of approximately 277 subjects will be enrolled. When follow-up is complete for the primary analysis based on 12-month follow-up, the data base will be locked. Information post-12 months will remain fully confidential until completion of 18-month follow-up. By pre-specification, a hierarchical analysis will be performed where the treatment effect on the rate of GA growth over 18 months will be statistically assessed if statistical significance is achieved on the rate of GA growth over 12 months.

[REDACTED] the primary analyses will be based on comparisons of Zimura™ 2 mg vs the Sham control, and Zimura™ 4 mg vs Sham control. For the comparison of Zimura™ 2 mg vs Sham control, the 26 subjects randomized to Zimura™ 2 mg and 26 subjects randomized to Sham control from Part 1 will be combined with the 40 subjects randomized to Zimura™ 2 mg and 80 subjects randomized to Sham control from Part 2, where the analysis will be stratified by Part 1 vs Part 2. The comparison of Zimura™ 4 mg vs Sham control will be based on the 80 subjects randomized to each of these two arms in Part 2.

The primary analysis [REDACTED] for each of the two pairwise comparisons of an active dose of Zimura™ vs the Sham control is formally based on a three-category decision guideline. To be specific, the decision guideline for this trial is based on whether the estimated reduction in rate of GA growth over 12 months for a dose of Zimura™ versus Sham control is less than 14%, is from 14% up to 24.5%, or is at least 24.5%.

Note that these categories should not be interpreted as providing strict decision rules but rather as guidelines that will be factored into a broader scientific assessment of the benefit to risk profile of the Zimura™ dose regimen. This broader assessment will include consideration of safety, of supportive efficacy endpoints, and of relevant information external to this trial. Specifically, the decision guidelines for this trial are:

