## 8.6 CLINICAL LABORATORY DETERMINATION

- All laboratory data will be listed and values falling outside normal ranges will be identified, whether they will be deemed clinically relevant or not.
- Laboratory data will also be summarized in tables presenting values at each scheduled visit up through the month 12 visit
- Value changes from Baseline to each scheduled visit up through the month 12 visit
- A summary table of all analytes with the Baseline mean and the mean change from Baseline to the last value observed
- A summary table of all analytes with the Baseline median and the median change from Baseline to the last value observed

for the following parameters: hematological parameters (hemoglobin, white blood cells, platelets, neutrophils (absolute numbers), lymphocytes (absolute numbers), monocytes (absolute numbers), eosinophils (absolute numbers), basophils (absolute numbers), renal function parameters (serum creatinine and BUN), hepatic function parameters (serum bilirubin, alkaline phosphatase, GGT, SGOT/AST and SGPT/ALT), electrolytes (sodium, potassium, chloride, bicarbonate, calcium and phosphate), urinalysis parameters (complete urinalysis including specific gravity, protein, blood, etc.).

The incidence of subjects with "Notable Laboratory Values" after the first dose of study drug will be evaluated using the criteria for Notable Laboratory Values given below. Only data collected in the first year after the first dose of study drug, up to the laboratory data taken at the Month 12 visit (before Month 12 treatment is administered) will be included; if there is no Month 12 visit, data will be included up to a target of 365.25 days after date of first dose, or 30 days after the last dose of study drug, whichever is later.

By-subject listings of all notable laboratory values will also be provided; for each subject who has an analyte with a notable value, all values of that particular analyte taken during the study will be presented in the listing, and the notable value, and any values outside of normal limits, will be identified.

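### SAP 8.2's fallback end of the first year does not limit the last injection to those before Month 12, so a subject who misses only that dose and resumes has adverse events counted well past one year

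*SAP*

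**What the plan says.** SAP 8.2 sets the main rule: "First year will be defined as starting after the first dose of study drug until prior to the first injection at Month 12". The fallback opens with "If a Month 12 injection does not exist, the end of first year is defined as the Month 12 visit". The rest of that sentence, which takes the later of the dates it names, contains "or target of 365.25 days after the date of first dose if no Month 12 visit) or 30 days after the last injection, whichever". The trigger is the absence of a Month 12 injection. It is not the end of treatment.

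The treatment-emergent definition in the same section runs "up to and including 30 days after the last dose of study drug, within the first year as defined above". It therefore refers back to the first-year end date and adds no limit of its own. The definition of first-year adverse events refers back in the same way. SAP 8.3 summarizes treatment-emergent serious events on this basis.

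SAP 8.6 has a parallel rule for notable laboratory values. If there is no Month 12 visit, data are included up to day 365.25 "or 30 days after the last dose of study drug, whichever is later".

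Three other statements bear on the point:
- The Protocol synopsis states "Subjects randomized to active drug will receive 18 doses of Zimura™", and the visit schedule in Protocol 10.2.3 lists injections through Month 17.
- SAP section 1 limits the plan to the one-year data.
- Protocol 11.3 states "Information post-12 months will remain fully confidential until completion of 18-month follow-up".

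**The concern.** The fallback suits a subject who stopped treatment before Month 12: the last dose is then early, and adding 30 days gives a sensible end of observation. It does not suit a subject who missed the Month 12 injection alone and was dosed again afterwards. That subject's last injection lies in the second period of the trial, and the later-of rule moves the end of the first year there with it.

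Two things are at stake. First, SAP 8.2 and 8.3 plan numbers and percentages of subjects with events, with no adjustment for exposure. A longer window for some subjects can only add events to these tables, and nothing offsets it. Second, a 12-month report would include events from after Month 12, outside the SAP's stated scope and contrary to Protocol 11.3. Such data may exist at the 12-month lock: Protocol 9.1.2 provides for Part 1 subjects who already have 18 months or more of treatment.

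**Working it through.** This is date arithmetic. Days are counted from the first dose.

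**Inputs**
- Month 12 target: 365.25 days (SAP 8.2), so one month = 365.25 / 12 = 30.4375 days.
- Planned doses: 18 (Protocol synopsis).
- Visit window: ±7 days (Protocol 10.2.3).
- Minimum interval between doses: 21 days (Protocol 9.1.2).
- Size of the 4 mg arm: 80 (Protocol 11.3).

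**Check against the plan's own figure.** Day 1 plus Months 1 to 17 gives 1 + 17 = 18 doses, as stated. The last scheduled injection is therefore at Month 17; the Month 18 list has none.

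**Fallback end date.** With a Month 12 visit on day 365.25, or no visit:

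end = max(365.25, last injection day + 30)

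| Last injection | Injection day | End of first year (day) | Beyond day 365.25 |
|---|---|---|---|
| Month 11 (stopped) | 334.8 | 365.25 | 0 |
| Month 13 (resumed) | 395.7 | 425.7 | 60.4 |
| Month 14 | 426.1 | 456.1 | 90.9 |
| Month 15 | 456.6 | 486.6 | 121.3 |
| Month 16 | 487.0 | 517.0 | 151.8 |
| Month 17 | 517.4 | 547.4 | 182.2 |

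For Month 17, 547.4 / 365.25 = 1.50, so the window is half as long again. With the ±7 days the end falls between day 540 and day 554. The first row shows that the rule works for a subject who stopped treatment; only those who miss Month 12 and resume are affected.

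**Weight in a table.** One affected subject dosed to Month 17 adds 182.2 days to an 80-subject arm's 80 × 365.25 = 29,220 days, or 0.6%. Four such subjects (5% of the arm) would add 2.5%, and eight (10%) would add 5.0%. These counts are illustrations; the documents give no rate.

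**Do the visit windows force a missed Month 12 dose?** Month 11 given 7 days late is day 334.8 + 7 = 341.8. Month 12 taken 7 days early is day 358.25, only 16.4 days later and short of 21. But 341.8 + 21 = 362.8, and the Month 12 window stays open until day 372.25. That leaves 372.25 − 362.8 = 9.4 days in which both rules are met, so the dose is not forced out.

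**Laboratory rule (SAP 8.6).** After Month 12, scheduled laboratory tests occur only at Month 18 or early withdrawal. Nominal Month 18 is 18 × 30.4375 = day 547.9, just after the extended cut at day 547.4. A Month 18 sample enters only if drawn by the cut; otherwise the rule admits early-withdrawal or unscheduled samples.

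**The case against.** The best defence is context. The SAP is for one-year data, SAP 8.2 restricts its tables to first-year events, and Protocol 11.3 keeps later information confidential. On that reading, the last injection naturally means the last one within the first year, and a careful programmer would apply it so. This is probably what was meant. But those statements set no per-subject cut-off, and the definitions that mention the first year point back to the same uncapped date. Protocol 11.6.1 requires the details to be fixed before unmasking, so the intent should be written down.

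It can also be said that few subjects will reach the fallback, and this stands. SAP 3.4.2 lets some unscheduled visits substitute for missing scheduled ones, with details in Appendix 1, whose content was not available for this review. A delayed injection might therefore be assigned to Month 12. No visible text bars resuming after a missed dose, but parts of Protocol 9.1 are redacted, so resumption is an assumption.

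A reader might infer more than the documents support:
- *That the protocol itself produces missed Month 12 injections*, through the rule "Monthly doses should be administered at least 21 days apart" combined with the visit windows. It does not; more than 9 days of the window remain usable.
- *That raised intraocular pressure triggers the fallback.* Protocol 7.2 holds back only the second injection of the day, while SAP 8.2 cuts at the first Month 12 injection. A subject whose second injection is delayed or omitted still has a first one.
- *That the extra follow-up depends on tolerability and so differs by arm.* This is possible, but nothing visible describes withholding a whole monthly dose for an adverse event and later resuming.

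**Conclusion.** The wording gives a wrong result in one identifiable case and should be corrected. A subject who misses only the Month 12 injection and resumes has a first year that ends between about day 426 and about day 547, against about day 365 for others: an excess of roughly 60 to 182 days. The upper figure assumes on-schedule dosing through Month 17, with follow-up that far available at the data cut. A Part 1 subject dosed beyond 18 months could exceed it.

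The practical weight is low. The number affected is unknown and probably small, the tables are descriptive with no test attached, and the error over-counts events rather than losing them. No efficacy conclusion is touched. The documents do not support a claim of biased comparison between arms, or that confidentiality will in fact be breached. They show only that the literal rule would permit post-Month-12 events in the 12-month tables. The laboratory rule has the same gap with less consequence.

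**What to change.** In SAP 8.2, for a subject without a Month 12 injection, let T be the date of the Month 12 visit, or day 365.25 if there was no visit. End the first year at the later of T and 30 days after the last injection given before T, and in any case no later than just before the first injection after T. Apply the same limit in SAP 8.6, where T is day 365.25 because the rule there applies only when there is no Month 12 visit.

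With T at day 365.25, a subject who misses Month 12 and resumes at Month 13 has a first year ending at day 365.25, or at day 341.8 + 30 = 371.8 if Month 11 was 7 days late. Subjects who stopped before Month 12 keep exactly the window they have now, because their last injection already precedes T.

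The cost is one sentence in each of the two sections and a small derivation change before database lock. No new data are needed.

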#### **10.2.3.2 Day 3 ( $\pm 1$ day)**

- Telephone call to subject to ensure there are no signs or symptoms of retinal detachment or endophthalmitis.

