### 8.3 SERIOUS ADVERSE EVENTS AND DEATHS

- Treatment-Emergent Serious adverse events (SAEs) will be summarized by system organ class and preferred term. The number and percentage of the subjects who experienced at least one SAE will be included.
- SAE data will be evaluated for each treatment group (Zimura 4 mg, 2 mg, and 1 mg).
- Tabular summaries of the following SAEs will be provided:
  - All SAEs regardless of the relationship to study treatment
  - SAEs related to study treatment
  - SAEs related to injection procedure
  - Ocular SAEs (study eye) regardless of the relationship to study treatment
  - Ocular SAEs (study eye) related to study treatment
  - Ocular SAEs (study eye) related to injection procedure
- In addition, separate listings will be created for deaths and all SAEs. List for SAEs will include the subject identifier, age, sex, verbatim term, preferred term, eye (N/A/OD/OS/OU), serious (yes/no), date of onset, relative study day of onset, onset before

injection, after first injection or after second injection, duration of the event (or continuing), severity (mild/moderate/severe), causality (relationship to study medication/injection procedure), action taken (study drug permanently discontinued: yes/no), treatment (yes/no), and outcome (resolved/unresolved/fatal).

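### SAP 8.2 defines ocular TEAEs by one system organ class plus one preferred term, not by the recorded eye, so eye events coded elsewhere are left out of the tables titled Ocular TEAEs and, presumably, Ocular SAEs

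*SAP*

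**What the plan says.** SAP 8.2 gives the rule: "Ocular TEAEs have been defined as TEAEs linked to the" Eye Disorders SOC, with the preferred term Intraocular pressure increased added. No other term is added, and the affected eye is not part of the rule.

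The eye is nevertheless recorded. The adverse event listings in SAP 8.2 carry "eye (N/A/OD/OS/OU), serious (yes/no), date of onset" among their columns, and the SAE listing in SAP 8.3 has the same eye column.

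SAP 8.2 then plans tables under the ocular label, for example "Injection procedure related Ocular TEAEs by study eye and fellow eye". SAP 8.3 plans tables such as "Ocular SAEs (study eye) regardless of the relationship to study treatment" without saying what ocular means for SAEs. SAP 8.2 also plans a second overview giving the "overall summary of TEAEs by the categories" Study Eye, Non-Study Eye and Non-Ocular, and does not say how an event is assigned to one of the three.

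**The concern.** The treatment is a monthly injection into one eye, so the study-eye tables are where a reader looks first for harm from the drug or the procedure. The SAP's one-term addition is its own evidence that an event in the eye can fall outside the Eye Disorders SOC. It admits that single term and gives no general rule for any other event in the same position.

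The protocol shows which eye events it watches for. After each injection (Protocol 10.2.3.2 onward) it requires a "Telephone call to subject to ensure there are no signs or symptoms of retinal detachment or endophthalmitis". Protocol 12.2 also asks for each event to be attributed to the injection procedure or to the study drug. If a serious eye event is coded to another SOC, the tables meant to show it by eye, by severity and by attribution would omit it. A reader could then take a zero in a study-eye SAE table to mean that no serious event occurred in the study eye.

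**Working it through.** No sample size, error rate or event count in the documents depends on this rule, so there is no figure to reproduce. The check is to apply the rule to each kind of event and to each planned output.

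**Kinds of event**

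| Event | In the ocular set under SAP 8.2? |
|---|---|
| Eye event with Eye Disorders as its primary SOC | Yes |
| Intraocular pressure increased | Yes, by the named addition |
| Eye event with another primary SOC and a secondary link to Eye Disorders | Depends: the word for the link does not say primary only or any |
| Eye event with no link to Eye Disorders | No, on either reading |

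The last row is left out however the sentence is read. The third row could be programmed either way.

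**Outputs**

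1. Tables titled Ocular TEAEs (SAP 8.2):
   - three by study and fellow eye (all, treatment-related, injection-procedure-related);
   - three for the study eye by maximum severity (the same three groupings);
   - one for the study eye on discontinuation of study drug.

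   That is 3 + 3 + 1 = 7 tables, all governed directly by the definition.
2. Tables titled Ocular SAEs (SAP 8.3): three for the study eye (all, treatment-related, injection-procedure-related). No separate definition is given, so the 8.2 rule presumably carries over. This is an inference.
3. Cataract table (SAP 8.2): selected by high level term and then split by eye. It does not depend on the ocular definition.
4. Second overview (SAP 8.2): split into three eye categories with no stated rule. If it uses the eye field, an event can be counted under Study Eye there and be absent from the Ocular TEAE tables. If it uses the SOC rule, the same event falls under Non-Ocular although its recorded eye is OD, OS or OU.
5. All-event tables (SAP 8.2 and 8.3): all TEAEs, treatment-related, injection-related, by severity, leading to discontinuation or death, and the SAE tables. They keep every event in their category by SOC and preferred term, without an eye split.
6. Listings: they keep every event, with the eye shown.

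The definition therefore affects seven tables directly and three by inference. One further output may disagree with them.

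**Does the replacement rule lose anything?** Take as ocular every event with eye OD, OS or OU, plus every Eye Disorders or Intraocular pressure increased event whose eye is missing or N/A. If links to the SOC are read the same way under both rules, every event in the present set has either a recorded eye (first part) or none (second part). The new set therefore contains the present one, and the ocular set can only stay the same or grow.

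**The case against.** Several points on the other side stand.

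- A reader might infer that misplaced events disappear from all eye-specific output. The documents do not support this. The cataract table has its own selection rule, the second overview has none stated and may already use the eye field, and the ocular SAE tables inherit the rule only by inference.
- A reader might infer that a serious eye event could vanish from the report. It could not. It would appear by name in the all-TEAE and SAE tables, in the related or injection-related tables where applicable, and in the listings with its eye.
- Adverse event tables are not the only view of eye safety. SAP 8.5 plans shift tables for anterior chamber cells, vitreous haze, vitreous haemorrhage and peripheral retina, monthly and from before to after injection. These are examination findings, not event counts.
- If any link to Eye Disorders counts, fewer events are lost, and the single added term could be the only one its authors found unlinked. The documents neither confirm nor exclude this.
- A reader might want a size from an assumed incidence. That would give the chance that an event occurs, not the chance that it is misclassified.
- An Eye Disorders rule extended by a fixed list of ocular terms from other SOCs would also work.

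These points limit the reach of the defect but do not remove it. The all-event tables have no eye split, so a study-eye count that includes a misplaced event would have to be rebuilt from listings, unless the overview happens to use the eye field. The unclear meaning of the link is itself a reason to rewrite the sentence, since two programmers could produce different tables from it.

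**Conclusion.** The point holds for the tables titled Ocular TEAEs and, by inference, for those titled Ocular SAEs. The stated rule ignores a field recorded for every event and can only undercount eye events relative to that field. No endpoint, error rate or decision threshold is involved. What is at stake is the completeness of the study-eye safety tables and their agreement with the overview.

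The number of events affected cannot be derived from the documents. It depends on which terms MedDRA places outside Eye Disorders and on whether secondary links count. It could be zero. The conclusion assumes that the eye field is completed reliably and, for the three SAE tables, that SAP 8.3 uses ocular in the sense of SAP 8.2. The change is worth making because it gives consistent tables under any coding.

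**What to change.** Replace the definition in SAP 8.2 with one rule. An ocular TEAE or SAE is any such event with recorded eye OD, OS or OU, regardless of SOC, plus any Eye Disorders or Intraocular pressure increased event whose eye is missing or N/A. Assign study or fellow eye from the same field. State that the rule applies to the seven ocular TEAE tables, the three ocular SAE tables in 8.3 and the second overview.

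If the SOC approach is kept instead, state whether secondary links count, list in advance the ocular terms taken from other SOCs, and apply that rule to the same outputs.

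The cost is one SAP sentence, some added programming and a review of the eye field for missing or inconsistent entries. No new data are needed. The change should be made before unmasking, in line with Protocol 11.6.1.
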